That population will yield a subset with advancing but asymptomatic disease. Within that sub-population a group will exist who will proceed to diagnosis and be willing to learn about clinical trials. By measuring this response the effectiveness of the messaging about engaging diagnosis and follow up can be shown. There is not comparable data so this will establish a baseline.

A separate track will be to measure the number of participants who enter the diet and lifestyle education programs. Measuring this response will also establish a baseline measure for the effectiveness of this messaging and inform future efforts.

Overview

Research has shown that there is a high incidence of undiagnosed fibrosis within comorbid populations as a result of the frequently asymptomatic course of NASH

development. (<https://www.ncbi.nlm.nih.gov/pmc/articles/PMC4542082/>)
Liver disease is a dangerous and expensive problem to manage medically with the cost of NAFLD estimated to exceed \$32 billion per year.

(<https://www.sciencedaily.com/releases/2018/07/180703105956.htm>)

Liver disease in the form of Nonalcoholic fatty liver disease (NAFLD) and nonalcoholic steatohepatitis (NASH) are rapidly increasing population health threats driven primarily by diet and lifestyle. Fibrotic liver disease, culminating in cirrhosis, is frequently asymptomatic so it is common for a patient to first learn of what is a life threatening condition by being told that they have cirrhosis. Management and treatment of cirrhosis is complex and very costly with few treatment options and the only current therapy being a very expensive transplant for end stage liver disease.

The position of the Fatty Liver Foundation is that this problem is magnified by the current American Association for the Study of Liver Disease, (AASLD), practice guidelines which do not advise routine screening for NAFLD. This is the policy:

Excerpts from the AASLD Practice Guidelines 2017:

(AASLD Diagnosis Mgt NAFLD Chalasani et al 2017 Hepatology)

- It can be argued that there should be systematic screening for nonalcoholic fatty liver disease, (NAFLD), at least among higher-risk individuals attending diabetes and obesity clinics.

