Under this protocol, no personally identifiable information will be captured. The consent form does require that it be personally signed but that information will not be digitized. Upon completion of the study the paper copy of the completed consent forms will be placed in secure storage.

The test will be assigned a randomly generated ID code which will be assigned to the consent form and to the demographic form. That code will connect the demographic information to the results of the test for analysis. In the event that a competent authority required the retrieval of the consent for the test, it would be possible, through the use of the ID code, to connect the information. At no time will the information be stored together or be in a compatible format.

The ID code will be keyed to the digitally stored FibroScan results database which the patient can provide to their physician at their discretion. The scans will not be personally identified and can only be accessed by the unique code. The dataset will be stored and encrypted and individual test results can only be retrieved using the random key code. In this way the patient can have access to the test result but only the patient will be in possession of the key that accesses the information.

Employees will be trained in the expectations of confidentiality and will have signed an agreement to keep any patient information private as part of the hiring procedure.

The FibroScan Test Procedure

FibroScan is notable for its fast, safe, non-invasive design. This is the procedure:

A certified FibroScan trained technician will administer the test.

- A pain-free diagnostic test, FibroScan® requires no sedation of any kind.
- The procedure itself usually takes about 5 minutes.
- For the procedure, the patient will lie on their back with their right arm raised behind their head and their right abdominal area exposed.
- The technician will apply a water-based gel to the skin and then place a non-invasive probe over the liver.
- During the exam, the patient may feel a slight vibration on the skin at the tip of the probe as it delivers ultrasound waves to the area for measuring purposes.

Risk/Safety Information

There are no uncommon risks or safety concerns resulting from this procedure. There will be the normal office space risks when accommodating patients with the common comorbidities

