The data from the study will be used to support future financial modeling and to provide baselines for programs to educate patients about clinical trials, diet, and lifestyle changes delivered electronically. Since there is no existing measure, an a-priori power analysis is not overly instructive, but based on an assumed normal distribution the study seeks to enroll no fewer than 400 participants to yield a minimum theoretical power of around 0.8 and may include up to a maximum of 1,000 patients.

The study will also produce data on the incidence and staging of NAFLD and NASH, as indicated by their FibroScan scores, and will track, in aggregate, their response to information about clinical trials and dietary support delivered through online resources. This data will not be informed by the patient record as no personally identifiable data will be collected.

The dataset will include demographic information and general ethnicity so aggregate subtotals of the various populations may be examined for additional insights to inform future investigations.

DATA COLLECTION:

Demographics:

After signing the consent form the research subjects will fill out a basic form to provide demographic information, including sex, age, and race/ethnicity. We will measure height and weight prior to CAP/FibroScan testing.

Metabolic Syndrome:

Subjects will use a form to check YES or NO for comorbid components of the metabolic syndrome that they may or may not have:

- Obesity/overweight
- Diabetes mellitus
- Hypertension
- Hypercholesterolemia
- Hypertriglyceridemia
- Gout or elevated uric acid

Other Health Conditions:

Subjects will use a form to check YES or NO for other health conditions they may or may not have:

- Heart disease
- Heart attack
- Arrhythmia
- Stroke
- Arthritis
- Osteopenia/osteoporosis
- Hypothyroidism
- Low Vitamin D
- Low testosterone
- Menopausal state
- Inflammatory bowel disease (ulcerative colitis or Crohn's disease)
- Cancer
 - Skin: melanoma
 - Skin: basal cell or squamous cell cancers
 - Other type of cancers: lymphoma; leukemia; head or neck; thyroid; brain; breast; lung; stomach; colon; liver; ovary; uterus; prostate; bone

Diet:

Subjects will fill out a form using a 5-point scale of the frequency of their average weekly dietary intake of specific food types: (A. 0 days, B. 1-2 days, C. 3-4 days, D. 5-6 days, E. 7 days per week)

- Proteins: eggs, cheese, beans, fish, chicken, turkey, beef, pork

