Subjects will be asked to complete a survey about their experience after having the CAP-FibroScan and hearing their results, using a 5-point scale: very likely—likely—neither likely nor unlikely—unlikely—very unlikely.

1. Having completed the CAP-FibroScan and obtained your results, how likely are you to:
 - recommend this test to a friend or family member?
 - share your results with your doctor?
 - consult with a liver specialist?
 - seek information about FDA-approved clinical trials of therapies for non-alcoholic fatty liver disease?

Subjects will be asked to assess their level of satisfaction with the CAP-FibroScan procedure after being informed of their results, using a 5-point scale: very satisfied—satisfied—neither satisfied nor dissatisfied—dissatisfied—very dissatisfied.

2. Having had the CAP-FibroScan and obtained your results, how satisfied are you with the procedure?
 - a. If you answered very satisfied or satisfied, please check all the reasons for your answer:

- Ease of scheduling appointment for procedure.
 - Scheduled procedure occurred on time.
 - Cleanliness of the facility.
 - Professionalism and friendliness of staff.
 - Understandable explanation of the procedure and sufficient answers to my questions.
 - Quality of explanation of the results and quality of the answers to your questions about the results.
 - Comprehensive discussion of options my future care.
- b. If you answered dissatisfied or very dissatisfied, please check all the reasons for your answer:
- Lack of ease of scheduling appointment for procedure.
 - Procedure did not occur on time.
 - Problems with the cleanliness of the facility.
 - Problems with the professionalism or friendliness of staff.
 - Inadequate explanation of the procedure and deficient answers to my questions.
 - Inadequate explanation of the results and deficient answers to my questions about the results.
 - Inadequate discussion of options for my future care.
3. Having had the CAP-FibroScan and obtained your results, how satisfied are you that the procedure provided useful information about your health?
- a. If you answered very satisfied or satisfied, please check all the reasons for your answer:
- I understand what the CAP-FibroScan measures.
 - I understand how much fat I have within my liver.
 - I understand if I have or do not have evidence of scarring (fibrosis) of my liver.
 - The results gave me a better understanding of my liver health.

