 - No fat but evidence of liver stiffness
 - Fat without liver stiffness
 - Fat with liver stiffness
 - Stiffness values indicative of cirrhosis
 - Stiffness values indicative of fibrosis without cirrhosis

NOTE: no individual follow up or track will be done as not personally identifiable information will be captured or retained.

2. The secondary goal is to determine factors that are statistically significantly associated with the presence or absence of fat with or without increased liver stiffness.

We will analyze data using a standard statistical software package, Stata® 12.1 (Stata Corp, College Station, TX). We will express continuous variables using the mean ± standard deviation, and we will test the null-hypothesis using the Student t-test. We will compare categorical variables using contingency table analysis. For all statistical tests, we will define a two-sided p-value of ≤0.05 as statistically significant. We will perform multivariate analysis of all risk factors found to be statically significant (p ≤0.05) using univariate analysis.

This exploratory goal seeks to determine the degree of satisfaction of subjects who undergo a screening CAP-FibroScan free of charge.

We will calculate the frequency of answers for each of the five items reflecting subjects' likelihood of:

- recommending this test to a friend or family member.
- sharing their results with their doctor.
- consulting with a liver specialist.
- seeking information about FDA-approved clinical trials of therapies for non-alcoholic fatty liver disease.
-

We will not perform statistical analyses for these descriptive data.

Disease Staging

The disease staging to be analyzed will be based upon these breakpoints from the FibroScan test. The test scores will be translated into these staging ranges for analysis.

Transient Elastography (TE):

Disease	F0-F1	F2	F3	F4
NAFLD/NASH	≤ 7.0	≤ 7.5	≤ 10.0	≤ 14.0

Reference: Current Gastroenterology Reports. 2014; 16: 372

TE Interpretation: The subject's liver stiffness score in kPa units shows:

- **F0:** No liver fibrosis
- **F1-2:** Mild-Moderate liver fibrosis
- **F3:** Severe liver fibrosis
- **F4:** Cirrhosis

Controlled Attenuation Parameter:

Steatosis Grade	% Steatosis on Liver Biopsy	CAP Value
Mild (S1)	5-33%	225-275 dB/M
Moderate (S2) to Severe (S3)	>33% >66%	275-400 dB/M

Reference: World J Gastroenterol. 2016; 22: 7236

DATA COLLECTION

Demographics:

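### The Hypothesis claims to show how well the diagnosis and follow-up messaging works, but no planned measure records anyone seeking care and there is no comparator

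*Combined protocol and SAP*

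**What the plan says.** The protocol's Hypothesis section describes a subset with advancing but asymptomatic disease and states: "Within that sub-population a group will exist who will proceed to diagnosis and be willing to learn about clinical trials". It continues: "By measuring this response the effectiveness of the messaging about engaging diagnosis and follow up can be shown", and then: "There is not comparable data so this will establish a baseline".

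Four other places bear on whether this can be done:

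- **Protocol, CAP-FibroScan Experience and Satisfaction Survey.** "Subjects will be asked to complete a survey about their experience after having the CAP-FibroScan and hearing their results". Question 1 uses a five-point likelihood scale. One item is how likely the person is to "consult with a liver specialist"; another is sharing the results with their doctor.
- **Protocol, Intended Use of the Data.** The study "will track, in aggregate, their response to information about clinical trials and dietary support delivered through online resources". Seeking a diagnosis is not in that list.
- **SAP, Data Analysis, NOTE.** "no individual follow up or track will be done as not personally identifiable information will be captured or retained".
- **SAP, Data Analysis, exploratory goal.** The likelihood items are reported as answer frequencies with no statistical analysis, and no breakdown by scan result is specified.

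The sections on outputs for the patient and on the post-test step direct people to telemedicine or their own physician. Neither says that use of these routes will be counted.

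**The concern.** The Hypothesis makes two claims about the diagnosis step: that the response will be measured, and that measuring it will show the messaging to be effective. The first needs a record of what people did after the scan. The second also needs something to compare with, because an uptake rate in one group that all received the same messaging does not show what the messaging added.

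The step matters to the sponsor's own aims. The protocol wants data that could support a change in screening guidance, and it asks which populations justify screening on a cost-benefit basis. Whether an abnormal scan leads to contact with a clinician bears on both. A later programme that took the Hypothesis at its word would look in this study for a follow-through baseline that the planned data cannot supply.

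**Working it through.** The plan gives no figure for this step, so there is none to reproduce. The check is a trace of every planned data source, asking whether it records a step towards diagnosis after the scan.

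| Planned source | Where described | Records a consultation, telemedicine contact or diagnosis? |
|---|---|---|
| Intake forms (demographics, conditions, diet, exercise, alcohol, other liver disease) | Protocol and SAP, Data Collection | No; the intake form is completed before the scan |
| Height and weight | Same | No; measured before the scan |
| Scan (stiffness and CAP) | Protocol, Step 3; SAP, Disease Staging | No |
| Perceived value in dollars | Protocol, Step 4 | No; price only |
| Experience and satisfaction survey | Protocol, survey section | No; stated likelihood |
| Aggregate online uptake | Protocol, Questions Posed and Intended Use of the Data | No; trial education and diet support only |
| Operating costs | Protocol, Questions Posed | No |

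Result: 0 of 7.

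**Could follow-up fill the gap?** Not at the individual level, because the SAP note rules it out. The note does not rule out anonymous aggregate counts, but none is planned for diagnosis.

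**Is there a comparator?** No. All participants go through the same education and post-test process. The Hypothesis itself says no comparable data exist.

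**Do the intention items address the right group?** Not as planned. The Hypothesis concerns people with advancing disease, whereas the SAP reports answers over all participants. The random code is described for the consent form, the intake questionnaire and the scan. The documents do not say that it goes on the survey, so a split by stiffness may not be possible.

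**How much could a split table say?** The plan gives no expected proportion with elevated stiffness, so I assume 5%, 10% or 20%. With m people in that group and a true proportion of 50% (the widest case), the 95% half-width is 1.96 × √(0.5 × 0.5 / m).

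| Participants | Assumed share elevated | m | Half-width (percentage points) |
|---|---|---|---|
| 400 (planned minimum) | 5% | 20 | 21.9 |
| 400 | 10% | 40 | 15.5 |
| 400 | 20% | 80 | 11.0 |
| 1,000 (planned maximum) | 5% | 50 | 13.9 |
| 1,000 | 10% | 100 | 9.8 |
| 1,000 | 20% | 200 | 6.9 |

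For example, 1.96 × √(0.25 / 40) = 0.155. The table would be descriptive and imprecise, but it would concern the people the Hypothesis names.

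**The case against.** The strongest reply is that this is narrative wording, not a defective analysis. Proceeding to diagnosis is not among the protocol's listed questions, nor is it a primary or secondary goal in the SAP. The Hypothesis admits that comparable data are lacking and claims only a baseline. The SAP already labels the survey items as likelihoods, under an exploratory goal about satisfaction. All of this stands, and it limits the point to what the Hypothesis claims. It does not remove the mismatch, because the Hypothesis still says effectiveness can be shown.

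A reader might infer more than the documents support, in four ways:

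- **That intention will be reported as if it were the diagnosis baseline, and will overstate it.** No section links the survey percentages to that baseline, and the documents contain nothing from which to estimate a gap between intention and action.
- **That the survey is certainly done at the screening visit.** It is placed after the results are heard, and no later contact is described, but no time or place is given.
- **That nothing in the claimed response is measured.** The clinical-trial part has a behavioural measure, enrolment in further education, and the separate diet track also has an uptake count.
- **That logging retrievals of scans by code would give a minimum estimate of clinician contact.** The Confidentiality section says "individual test results can only be retrieved using the random key code", but it also lets patients open their own results. Retrievals would therefore include openings with no clinician involved and would miss patients who only show the printout. The error can run either way.

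**Conclusion.** The concern holds for the diagnosis component only. The Hypothesis claims that the effectiveness of the diagnosis and follow-up messaging can be shown and a baseline set. No planned source (0 of 7) records the behaviour, individual follow-up is excluded, and there is no comparator. What the study can provide is stated intention on two items, and as planned only over all participants.

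The SAP primary outcome is unaffected, as are the aggregate measures for trial education and diet support. The documents do not support saying that the study will pass intention off as behaviour, or by how much the two would differ. The conclusion rests on a reading of the text and needs no numerical assumption. Only the cell sizes and half-widths above depend on the assumed 5% to 20% with elevated stiffness. The correction should be made because the claim exceeds the design and restating it costs almost nothing.

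**What to change.** 1. **Protocol, Hypothesis.** Delete the statement that effectiveness of the diagnosis and follow-up messaging can be shown. Say instead that, for diagnosis, the study describes participants' stated intention to consult a specialist or share results with a doctor, and does not measure whether they do so. Leave the trial-education and diet measures as they are.
2. **SAP, Data Analysis.** Put the random code already used for the intake form and scan on the survey as well. Tabulate the two items by stiffness category, with counts and denominators, as a descriptive table.

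The cost is a more modest claim, a few changed sentences, one code field on the survey and one extra table. Cells in the elevated group will be small: 20 to 80 people at the planned minimum under the assumed shares.

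If the sponsor wants a behavioural baseline, an anonymous aggregate count of telemedicine contacts by result category, over the number scanned in that category, would be compatible with the SAP note. It should count first contacts only, and it would miss people who go to their own physician. It needs the telemedicine service's agreement to keep the count, which the documents do not address. It would describe uptake and would still not show effectiveness.

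Code retrievals could serve only as an imprecise proxy. Before any such log is used, the SAP note and the Confidentiality text would have to be reconciled with it, since the same code is also on the signed consent form.
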